All data processing and analysis in the study will be conducted within the secure IT environment of the Clinical Informatics Research Group, at the University of Surrey. The information security policies and procedures of the Research Group have been approved by the NHS Digital as meeting Information Governance Toolkit (IGT) standards^{xii}.

The system is continuously being updated and modernized in respect of information processing, security and governance processes. The data are automatically extracted from the network of GP practices using a Simple Object Access Protocol (SOAP) web service, on a weekly basis. Data are uploaded to a secure Microsoft SQL server, and processed into aggregated tables; these are then linked to a pre-defined report structure using business intelligence software (Tableau Software, Inc. Seattle, WA, www.tableau.com), to produce a weekly surveillance report in a timely manner.

Using the EHR system, routine data as well as the content of encoded ADR cards will be extracted using methods that Surrey developed and deploys to extract RCGP RSC surveillance data. Sensitive coded data and free-text data will not be extracted. Only relevant EHR data for this study (e.g. disease or symptom, vaccination status and brand) coded by the GPs or other health professional will

¹ This is also referred to as “3DES”, which is the commonly used name for the triple data encryption algorithm (TDEA, also written Triple DEA) symmetric-key block cipher.

² RSA stands for Rivest, Shamir and Aldeman who founded RSA Laboratories. They created large numbers with only two prime factors, a core component of the encryption process

be extracted^{xiii}. Large volume of research that has come out of UK primary care is based on coded data^{xiv}. The quality of primary care data are such that the expectation will be able to detect frequent AEIs.^{xv}

GP practices will be required to use the relevant Read code for ADR notifications, when recording data from a returned card (Read Code: PPD - Adverse drug reaction notification).

Relevant coded data will be extracted, however these are limited to the administration regime, AEIs and batch number fields of prescribing data.

The following routinely collected patient data will be extracted for the study:

- Demographic information: age, gender, ethnicity, date of registration.
- Seasonal influenza vaccine information: date of administration, brand and batch number when available

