The cumulative incidence rates (per 100 subjects) of AEIs within the 7 days post-vaccination period derived from the ADR card, with 95%CI, will also be tabulated for subjects who returned the ADR card.

The cumulative incidence rates (per 100 subjects) of AEIs within the 7 days post-vaccination period, with 95%CI, will also be tabulated for subjects from the RCGP RSC network of GP practices.

[figure not shown]
Schematic description of process from site selection to data extraction

A series of flow charts have been developed to facilitate understanding of recruitment flow, the training and other process that have to be developed as participating GP practices, and to explain the data flow in the practice.

[figure not shown]
The flow charts are presented below

Flow chart 1: Practice selection process

[figure not shown]
Flow chart 2: Preparation pre-study & site initiation process

[figure not shown]
Flow chart 3: Visits during study linked to data quality

Flow chart 4: Data capture flow chart – patient flu vaccinated in the surgery

[figure not shown]

Flow chart 5: Data capture flow chart – patient NOT vaccinated in the surgery

The added value of combining those two systems is to be able to enhance the collection of AEIs (using the customized cards) and ensure further that the data is comprehensively collected (using the routine EHR system).

Flow chart summarizing the automated data extraction process performed using Apollo system

Safety reporting, including routine pharmacovigilance

Safety reporting

An AE is any untoward medical occurrence in a patient or clinical investigation subject, temporally associated with the use of a medicinal product, whether or not considered related to the medicinal product.

An AEI is any untoward medical occurrence which follows immunisation and which does not necessarily have a causal relationship with the usage of the vaccine. The AEIs following vaccination may be any unfavourable or unintended sign, abnormal laboratory finding, symptom or disease. EMA recommendations regarding AEIs collected after vaccination in this study are specified in Appendix 2.

A Serious Adverse Event (SAE) is defined as any adverse event which is fatal, life threatening, disabling or incapacitating, requires in-patient treatment or prolongs existing hospitalization, is a congenital anomaly in the off-spring of the patient or which may require intervention to prevent the previously stated outcomes.

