Possible side effect or Condition in the 7 days after influenza vaccination	Start date of the symptom	Please tick as appropriate
Conjunctivitis – Sticky eyes	____/____/17	
Runny nose	____/____/17	
Blocked nose	____/____/17	
Epistaxis – Nose bleed	____/____/17	
Common cold	____/____/17	
Cough	____/____/17	
Sore throat	____/____/17	
Hoarse voice	____/____/17	
Wheezing	____/____/17	
Decreased appetite	____/____/17	
Nausea – feeling sick	____/____/17	
Vomiting – being sick	____/____/17	
Diarrhoea	____/____/17	
Fever (add temperature if measured)	____/____/17	
Allergic reaction (rash)	____/____/17	
Other allergic reactions	____/____/17	
Facial oedema (swelling)	____/____/17	
Local reaction to vaccine	____/____/17	
Rash	____/____/17	
Irritability	____/____/17	
Drowsiness	____/____/17	
Fatigue	____/____/17	
Tremor / shaking	____/____/17	
Seizure / fits	____/____/17	
Headache	____/____/17	
Muscle aches	____/____/17	
Joint pain	____/____/17	
Other		
1. _____	____/____/17	
2. _____	____/____/17	
3. _____	____/____/17	
Add below if more		

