3.4. Data extract from EHR

The following data from subjects in the 10 enrolled GP practices will be imported (anonymised) into the secure servers of the University of Surrey:

- Demographic information: age, gender, ethnicity, date of registration
- Seasonal influenza vaccine information: date of administration, brand and batch number when available
- Postcode: to understand any inequities in access according to level of social deprivation using Geographical Information System (GIS) methods. Full postcodes will be immediately transformed into deprivation scores, using the Index of Multiple Deprivation (IMD), within GP computer systems upon extraction
- Primary care consultations following vaccination, any other markers of health care utilisation, and referral to further care.
- Pre-specified European Medicines Agency (EMA) adverse events of interest (AEIs) ([Annex 2](#)) or any other reported AE recorded in the EHR. Only coded data (Read code and CTV3), i.e. where the GP codes a disease or symptom into the EHR system, will be extracted
- Data from at least one year prior to the start of the study to determine the category of UK Chief Medical Officer (CMO)-specified risk group for influenza vaccination the subjects belong to:
 - Life-style/risk factors – e.g. body mass index, smoking status
 - Records of other diseases and long term conditions – e.g. chronic respiratory disease, chronic heart disease, chronic kidney disease, chronic liver disease, chronic neurological disease, diabetes, immunosuppression, pneumonia, etc
- Pregnancy status during the course of the study period

No individual patient level data will be released to GSK.

GSK will be blind to GP practice identities, and the locality at which any AE occurs.

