7.3.2. Analyses of primary objectives

The weekly incidence rate (per 100 subjects) of any AEIs within 7 days* post-vaccination period reported via ADR card will be estimated by Vaccine group as follows in the Weekly vaccinated cohorts restricted to subjects who received the ADR card:

- The denominator will be the number of subjects in the Weekly vaccinated cohort for the week of interest who received the ADR card
- The numerator will be the number of subjects from the denominator who reported any AEIs on the ADR card within 7 days following vaccination with the seasonal influenza vaccine

**Day of vaccination plus the following 7 days*

The cumulative incidence rate (per 100 subjects) of any AEIs within 7 days post-vaccination period reported via ADR card will be estimated by Vaccine group as follows in the Cumulative vaccinated cohorts restricted to subjects who received the ADR card:

- The denominator will be the number of subjects in the Cumulative vaccinated cohort up to the week of interest who received the ADR card
- The numerator will be the number of subjects from the denominator who reported any AEIs on the ADR card within 7 days following vaccination with the seasonal influenza vaccine

Similarly, weekly and cumulative incidence rates will be estimated for the following AEIs within 7 days post-vaccination period reported via ADR card:

- Fever/pyrexia
- Fever $>38.5^{\circ}\text{C}$ and $>39.5^{\circ}\text{C}$ (with a temperature measurement recorded in EHR; independent of route of measurement)
- Local symptoms (i.e. local erythema)
- Any and each general non-specific symptom: drowsiness, fatigue, headache, irritability and malaise
- Any and each respiratory AE: conjunctivitis, coryza, cough, epistaxis, hoarseness, nasal congestion, oropharyngeal pain, rhinorrhoea, wheezing
- Any and each gastrointestinal AE: decreased appetite, diarrhea, nausea, vomiting
- Any and each sensitivity/anaphylaxis AE: anaphylactic reactions, facial oedema, hypersensitivity reactions
- Rash
- Any and each musculoskeletal AE: arthropathy, muscle aches / myalgia
- Any and each neurological AE: Bell's palsy, Guillain-Barre syndrome, peripheral tremor, seizure / febrile convulsions

Similarly, weekly and cumulative incidence rates of any SAEs within 7 days post-vaccination period reported via ADR card will also be generated.

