In addition, weekly and cumulative incidence rates of any AEIs, each AEIs category (i.e. fever/pyrexia, local symptoms, any general non-specific symptom, any respiratory, any gastrointestinal, any sensitivity/anaphylaxis, rash, any musculoskeletal and any neurological AEs) and SAEs within 7 days post-vaccination period reported via ADR card will also be generated by Age group (6 months to 5 years; 6 to 12 years; 13 to 17 years; 18-65 years; >65 years) and by UK CMO-specified risk status (at risk, not at risk).

95% confidence interval (CI) adjusted for clustering effect of GP practices will be computed on all estimated incidence rates (Clopper-Pearson exact CI modified for cluster data as described in [Annex 1](#)).

The design effects and the intra-cluster correlation coefficients will also be estimated as described in [Annex 1](#) for the estimated cumulative incidence rates of AEIs reported on the ADR card within the 7 days post-vaccination period for the Cumulative vaccinated cohort Weeks 35-48 restricted to subjects who received the ADR card.

7.3.3. **Analyses of secondary objectives**

All analyses described for the primary objectives (refer to Section [7.3.2](#)) will also be generated by Vaccine group for all subjects included in the Weekly vaccinated cohorts and the Cumulative vaccinated cohorts (i.e. whether or not they received the ADR card).

For the weekly incidence rates (per 100 subjects):

- The denominator will be the number of subjects in the Weekly vaccinated cohort for the week of interest
- The numerator will be the number of subjects from the denominator who reported the specified AEI within 7 days following vaccination with the seasonal influenza vaccine using data entered in the EHR (i.e. AEIs derived from ADR card and medically attended AEIs)

For the cumulative incidence rates (per 100 subjects):

- The denominator will be the number of subjects in the Cumulative vaccinated cohort up to the week of interest
- The numerator will be the number of subjects from the denominator who reported the specified AEI within 7 days following vaccination with the seasonal influenza vaccine using data entered in the EHR (i.e. AEIs derived from ADR card and medically attended AEIs)

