14. ANNEX 3 ADVERSE DRUG REACTIONS SOLICITED IN THE CARD

Possible side effect or Condition in the 7 days after influenza vaccination	Start date of the symptom	Please tick as appropriate
Conjunctivitis – Sticky eyes	____/17	
Runny nose	____/17	
Blocked nose	____/17	
Epistaxis – Nose bleed	____/17	
Common cold	____/17	
Cough	____/17	
Sore throat	____/17	
Hoarse voice	____/17	
Wheezing	____/17	
Decreased appetite	____/17	
Nausea – feeling sick	____/17	
Vomiting – being sick	____/17	
Diarrhoea	____/17	
Fever (add temperature if measured)	____/17	
Allergic reaction (rash)	____/17	
Other allergic reactions	____/17	
Facial oedema (swelling)	____/17	
Local reaction to vaccine	____/17	
Rash	____/17	
Irritability	____/17	
Drowsiness	____/17	
Fatigue	____/17	
Tremor / shaking	____/17	
Seizure / fits	____/17	
Headache	____/17	
Muscle aches	____/17	
Joint pain	____/17	
Other		
1. _____	____/17	
2. _____	____/17	
3. _____	____/17	
Add below if more		

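### The SAE rates that SAP 7.3.2 takes from the ADR card understate SAE incidence: the card records no outcome that defines an SAE, and unreturned cards count as no event

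*SAP*

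**What the plan says.** **The planned output.** SAP 7.3.2 ends its list of card-based AEI rates with "weekly and cumulative incidence rates of any SAEs within 7 days post-vaccination period reported via ADR card will also be generated". It then adds strata: "SAEs within 7 days post-vaccination period reported via ADR card will also be generated by Age group", and also by CMO risk status. The denominator is the vaccinated subjects who received a card, whether or not they returned it.

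**The definition.** The protocol's Safety reporting section reads "A Serious Adverse Event (SAE) is defined as any adverse event which is fatal, life threatening, disabling or incapacitating", and goes on to in-patient treatment, congenital anomaly and intervention to prevent such outcomes. The protocol glossary is also outcome-based. The SAP lists SAE only as an abbreviation.

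**The card.** Protocol Appendix 3 and SAP Annex 3 show the same table: a symptom, its start date, and a box headed "Please tick as appropriate". There are 27 listed symptoms and three free lines for anything else. The only listed row that asks for more than a date and a tick is "Fever (add temperature if measured").

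**The data route.** Under the protocol's data extraction section, "Sensitive coded data and free-text data will not be extracted". SAP 3.4 extracts coded disease or symptom data, and also "Primary care consultations following vaccination, any other markers of health care utilisation, and referral to further care". SAP 12.2.4 treats a subject with no reported event as having had none.

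**The cohorts.** SAP 6.3 and 6.4 admit only subjects registered from vaccination up to day 7. SAP 6.1 notes that people may leave a practice but does not mention death. The demographic extract in SAP 3.4 is "Demographic information: age, gender, ethnicity, date of registration"; neither date of death nor end of registration is named.

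**The concern.** A rate needs an instrument that can register the event. Here the event is defined by outcome and the instrument records symptoms. A ticked seizure or facial swelling may or may not have led to hospital, and the card cannot show which. The missing derivation rule and the non-report rule make this worse: what is not recognised or not returned is counted as absent.

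At stake is a set of SAE rates placed among the primary analyses of a safety surveillance study, which would come out low for reasons unrelated to the vaccine. A reader could take a near-zero card SAE rate as reassurance.

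The cohort rule raises a related question. Read literally, it could remove subjects who die inside the 7-day window, and death is the gravest of the outcomes that define an SAE.

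**Working it through.** **1. Can the card show an SAE?** The defining outcomes, set against the printed card:

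| Outcome in the protocol definition | Item on the card |
|---|---|
| Fatal | None |
| Life threatening | None |
| Disabling or incapacitating | None |
| In-patient treatment or prolonged stay | None |
| Congenital anomaly | None |
| Intervention to prevent the above | None |

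The code lists in Protocol Appendix 2 and SAP Annex 2 hold no code for seriousness, hospital stay or death. Seriousness could still reach the data if practice staff code a free-line entry, or if the linked utilisation and referral data are used. The SAP states no rule for either.

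**2. Direction.** Let p be the true SAE risk in card recipients, r the share of cards returned, and s the share of SAEs on returned cards that can be recognised as SAEs. If p is the same in returners and non-returners (an assumption), the expected card-only rate is p × r × s. Both r and s lie between 0 and 1, so the rate cannot exceed p. The EHR data include the coded card reports, so for the same subjects the card-only numerator cannot exceed the all-EHR numerator either.

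**3. The nearest figure in the plan.** The documents give no expected SAE rate. Protocol Table 1 has a row for 5,000 vaccinees and event probability 0.10%. It prints a 99.33% chance of at least one event and an RSE of 44.7%.

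- 1 − (1 − 0.001)^5000 = 0.9933
- √(0.999 / (5,000 × 0.001)) = 0.447

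Both reproduce. Table 1 assumes that every event is seen.

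**4. Illustration.** Take p = 0.1% (an assumption, not in the documents), 5,000 card recipients, and r = 0.5 from the roughly 50% return last season (Protocol 4a). The value of s is unknown, so the full range is shown.

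| r | s | Expected SAEs | Rate per 100 | Chance of at least one |
|---|---|---|---|---|
| 1 | 1 | 5.0 | 0.100 | 99.3% |
| 0.5 | 1 | 2.5 | 0.050 | 91.8% |
| 0.5 | 0.5 | 1.25 | 0.025 | 71.3% |
| 0.5 | 0.25 | 0.63 | 0.0125 | 46.5% |
| 0.5 | 0 | 0 | 0 | 0% |

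Return alone moves the 0.10% row of Table 1 to its 0.05% row (91.80%, RSE 63.2%). This shows the mechanism. It does not estimate the bias, because p and s cannot be taken from the documents. The number of card recipients will also be below the number vaccinated, since SAP 3.3.2 accepts that some vaccinees get no card.

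**5. Extent of the output.** There are 14 weekly and 14 cumulative rates. Week 35 and Weeks 35-35 are the same cohort, which leaves 27 distinct rates. The strata are overall, 5 age groups and 2 risk groups, so 8. The total is 27 × 8 = 216 distinct card-only SAE rates per vaccine group.

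**6. Deaths (conditional).** With S SAEs in N subjects, D of them fatal on days 0 to 7, excluding the deaths changes S/N to (S − D)/(N − D), which is lower whenever D > 0 and S < N. This applies only if death ends registration, which the documents do not say. They give neither S nor D, so I put no number on it.

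**The case against.** **Seriousness could come from the linked record.** Card entries are coded into the EHR with a card-source code, and utilisation and referral data are extracted. A card SAE could mean a card-reported event whose seriousness is judged from the record. This stands, and it rules out the tempting inference that the card rate must be exactly zero. It does not remove the downward bias, because unreturned cards still count as event-free. A rule that called certain symptoms serious by name could add false positives, but the SAP states none and it would depart from the outcome-based definition.

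**The study has other SAE sources.** SAP 7.3.3 and 7.3.5 give SAE rates from wider data, and the protocol requires SAEs deemed related to the sponsor's vaccine to reach the sponsor within 24 hours of awareness. SAEs are not a named endpoint and all analyses are descriptive. This also stands. A reader might infer that the study cannot see SAEs at all, and the documents do not support that. However, 7.3.3 and 7.3.5 lack a derivation rule too, and the 24-hour route yields no rate.

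**Non-return affects every card rate.** True. SAP 7.3.1 tabulates card return and 7.3.6.2 adds a returned-card analysis, but the latter covers AEIs and not SAEs.

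**Not everything was available.** The TFL annex is a separate document and the data-capture flow charts are not shown. Either could hold relevant detail. SAP section 7 nevertheless places the derivation rules in its Annex 1, which has none for SAEs.

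**The death point is conditional.** It is. SAP 7.1 tabulates exclusions with reasons, so such deaths might become visible, but they would not return to the rates.

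**Conclusion.** The point holds. The card-only SAE rates in SAP 7.3.2 are biased downward, by an amount the documents do not allow to be estimated. The direction rests on the printed card, the card-recipient denominator and the non-report rule. The halving at 50% return rests on last season's figure and on equal risk in returners and non-returners.

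Three stronger readings go too far: that the rate is necessarily zero, that it carries no information, and that the plan excludes deaths. The first two fail because coded free-line entries or linked data could supply seriousness. The third fails because no section says that death ends registration. The supported form is that, if it does, deaths on days 0 to 7 leave the SAE rates in 7.3.2, 7.3.3 and 7.3.5.

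This should be corrected, but it does not threaten the primary endpoint, which is AEI occurrence.

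A separate minor point: the card's instructions ask for severity and persistence, yet neither copy of its table shows a field for them. Severity is not seriousness, and a column could have been lost when the form was read, so this should be reported on its own.

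**What to change.** 1. **SAP 7.3.2 and 7.3.3.** Remove the card-only SAE rates from 7.3.2, including those by age and risk status. Section 7.3.3 has no SAE text of its own and only repeats 7.3.2 by reference, so the deletion alone would also lose the all-EHR 7-day SAE rates. Write these into 7.3.3 explicitly: weekly and cumulative, overall, by age group and by risk status. Keep 7.3.5. If the card-only rate is retained, label it as a lower bound that does not measure SAE incidence.
2. **SAP 12.2.4.** Add a rule that derives SAEs from the extracted data under the protocol definition. Confirm whether date of death is available, since the extract lists do not name it.
3. **SAP 6.3 and 6.4.** Keep subjects who die on days 0 to 7 in the cohort and count the death as an SAE. Leave the registration rule unchanged for those who leave alive. This settles the matter whichever way registration works.

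**Cost.** One card-only output is lost (216 distinct rates per vaccine group), and a few subjects with under 7 days of follow-up stay in the denominator. The rest is one derivation rule, an SAE paragraph in 7.3.3 and a sentence in each cohort definition. The SAP is dated 11 December 2017, after the planned vaccination period closed on 30 November, so the card cannot change for this season. The SAP text and outputs can.

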Groups eligible for flu vaccination are based on the recommendation of the Joint Committee on Vaccination and Immunisation (JCVI). The national flu immunisation programme aims to provide direct protection to those who are at higher risk of flu associated morbidity and mortality. This includes older people, pregnant women, and those with certain underlying medical conditions. In 2012 JCVI recommended extending vaccination to children to provide both individual protection to the children themselves and reduce transmission across all age groups by recommending an intranasal live attenuated influenza vaccine (LAIV).

In the UK, 2017/2018 influenza plan recommended the following groups to be vaccinated^v:

- all children aged two to eight (but not nine years or older) on 31 August 2017 (with LAIV)
- All primary school-aged children in former primary school pilot areas (with LAIV)
- Those aged six months to under 65 years in clinical risk groups
- Pregnant women
- Those aged 65 years and over
- Those in long-stay residential care homes
- Carers

In 2017/18 changes to the programme are as follows:

- **Morbidly obese:** Vaccination of the morbidly obese (defined as body mass index [BMI] of 40 and above) will attract a payment under the directed enhanced services (DES) in 2017/18.
- **Age segments in children to receive the seasonal vaccination (children aged 4-5 years):** These children will now be offered flu vaccination (LAIV) in reception class, rather than through general practice. No payment will be made under the DES if they are vaccinated in general practice (unless the child is in an at risk group);
- **School Year 4 (children aged 8-9 years):** As part of the phased roll-out of the children's programme, this year children in school year 4 will also be offered the vaccination.

Eligible adults aged 18 years and over will have the choice of getting their flu vaccine at a pharmacy the Community Pharmacy Seasonal Influenza Vaccination Advanced Service. Of note, the intent will be to issue cards to all vaccinated patients belonging the recruited practices, however, considering the UK influenza vaccination plan, some vaccinations are expected to occur outside of the GP settings describe as opportunistic vaccination, perform by third parties including pharmacist and thus it cannot be excluded that for some patients, ADR cards are not distributed. The AEIs will however be captured through the routine data collection process.

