3. STUDY DESIGN

3.1. Study design overview

- Type of design: prospective post-authorisation passive enhanced safety surveillance study in the United Kingdom (UK).
- Co-Sponsors: GSK and the University of Surrey, Guildford UK.
- Study vaccination period: intended to be from 01SEP2017 (start of the seasonal influenza vaccination) up to 30NOV2017.
- Study period: intended to be from 01SEP2017 (start of the seasonal influenza vaccination) up to 7 days after last study participant vaccinated.
- Study General Practitioner (GP) practices: 10 GP practices ordering mainly GSK's Fluarix Tetra vaccine for the 2017/18 season will be enrolled in the study before the start of the seasonal influenza immunisation season. These 10 GP practices will be selected based on their willingness to participate, their location (distributed across England (in London, a Northern city, and rural settings in the North and South)) and that the participating population spans different age strata, different levels of deprivation, different ethnic mix, different brand of computerised medical record systems, and different practice sizes. GP practices will also be included based on their ability to comply with the study protocol requirements.
- Study participants: subjects who receive influenza vaccination between 01SEP2017 and 30NOV2017 in the 10 enrolled GP practices and who have not opted-out of data sharing.
- Number of subjects: according to the sample size assumption (conservative approach), it was estimated to be able to reach a number of 50,000 subjects registered in the 10 enrolled GP practices with an estimate of 5,000 vaccinated subjects with 7 days of follow-up after vaccination.
- **Type of study:** self-contained.

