3.3.2. Adverse Drug Reaction card

In order to facilitate the coding of data using a standardised approach, the 10 enrolled GP practices will also distribute an ADR card to their subjects receiving seasonal influenza vaccine or, as appropriate, to their parent or carer.

Subjects will be instructed to record adverse events (refer to [Annex 3](#)) within 7 days following vaccination and to return the card to their GP practice not later than 14 days post-vaccination. Data recorded on these cards will then be recorded by the GP staff into the subject's EHR. The coding will follow a standardised approach to data recording (refer to [Annex 2](#)) and will include a specific code to indicate that the information is derived from those cards.

Of note, the intent will be to issue cards to all vaccinated patients belonging to the enrolled GP practices, however, considering the UK influenza vaccination plan, some vaccinations are expected to occur outside of the GP settings. These are described as opportunistic vaccination, performed by third parties including pharmacists and thus it cannot be excluded that for some patients, ADR cards will not be distributed. These vaccinations will still be encoded in the EHR and those subjects will be included in the study. The adverse events (AEs) will be captured through the routine data collection process (refer to Section 3.3.1).

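### The secondary and weekly brand rates pool subjects with and without an ADR card, so unequal card receipt between vaccine groups can look like a difference in reactogenicity

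*SAP*

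**What the plan says.** - **Secondary rates.** SAP 7.3.3 repeats the primary analyses by vaccine group in all vaccinated subjects, "whether or not they received the ADR card". One numerator counts both card-derived and medically attended AEIs.
- **Weekly rates.** SAP 9.1.1 also uses all subjects vaccinated in the week as denominator and EHR data for the numerator, overall and by brand.
- **Primary rates, for contrast.** SAP 7.3.2: "The denominator will be the number of subjects in the Weekly vaccinated cohort for the week of interest who received the ADR card".
- **Who may lack a card.** SAP 3.3.2 says of vaccination outside the practice, including by pharmacists, that "it cannot be excluded that for some patients, ADR cards will not be distributed". It continues: "These vaccinations will still be encoded in the EHR and those subjects will be included in the study". Their events come through routine data collection. Protocol section 4 gives the main adult route: "Eligible adults aged 18 years and over will have the choice of getting their flu vaccine at a pharmacy".
- **Who issues cards.** The enrolled sites, described in SAP 3.1 as "10 GP practices ordering mainly GSK's Fluarix Tetra vaccine".
- **Non-reporters.** SAP 12.2.4 treats a subject with no reported event as having had none.
- **Card receipt.** SAP 7.3.1 tabulates receipt and return by vaccine group. Neither document uses receipt to split or adjust the secondary or weekly rates.

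**The concern.** The pooled rate mixes two intensities of ascertainment. A card holder is prompted with a symptom list and can report a mild reaction without seeing anyone. A subject without a card contributes an event only if it reaches the record through routine care. Otherwise that subject adds to the denominator as event-free. The Protocol introduction itself describes the card as the enhancement over routine surveillance, so unequal capture is a premise of the design.

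The mix matters once it varies by brand. Cards come from practices selected for ordering mainly Fluarix Tetra. The documents describe no such selection for outside vaccinators. Receipt may therefore be associated with vaccine group, and the secondary objective is expressly presented as Fluarix Tetra versus others. The study exists to detect a rise in expected reactions quickly. A brand gap, or a change over weeks within a brand, could reflect who was given a card. The same mechanism could hide a real rise in a group with low receipt.

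**Working it through.** **Figures in the plan.** The documents give no card receipt by vaccine group, no brand mix outside the practices and no share vaccinated outside, so there is no stated figure for this bias to reproduce. The nearest is the precision in Protocol Table 1. For 5,000 vaccinated subjects and a 1% AEI probability, RSE = √((1−p)/(np)) = √(0.99/50) = 14.1%, and the Clopper-Pearson limits are 0.74% to 1.32%. Both agree with the table (14.1%; 0.7% to 1.3%).

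**Simple mixture, equal true risk in both groups.** Pooled rate = c × p₁ + (1 − c) × p₀, where c is card receipt. All inputs are assumed: p₁ = 5% with a card, p₀ = 0.5% without.

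| Receipt, Fluarix Tetra / others | Fluarix Tetra | Others | Ratio |
|---|---|---|---|
| 95% / 95% | 4.775% | 4.775% | 1.00 |
| 95% / 75% | 4.775% | 3.875% | 1.23 |
| 95% / 50% | 4.775% | 2.750% | 1.74 |
| 75% / 95% | 3.875% | 4.775% | 0.81 |
| 50% / 95% | 2.750% | 4.775% | 0.58 |

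For example, 0.95 × 5% + 0.05 × 0.5% = 4.775%, and 0.75 × 5% + 0.25 × 0.5% = 3.875%.

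**Second model, using the documented return rate.** Pooled rate = m + (1 − m) × r × q × a.

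- q = 50%, the approximate card return in the previous season (Protocol section 4).
- Assumed: a = 10% of returners report an AEI; m = 1% have a medically attended AEI, independent of card reporting; receipt r = 90% for Fluarix Tetra.

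Fluarix Tetra: 0.01 + 0.99 × 0.90 × 0.50 × 0.10 = 5.455%. For others:

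| Receipt, others | Rate, others | Ratio | Ratio range, a 5–20%, m 0.5–2% |
|---|---|---|---|
| 90% | 5.455% | 1.00 | 1.00 |
| 70% | 4.465% | 1.22 | 1.13–1.27 |
| 50% | 3.475% | 1.57 | 1.30–1.73 |
| 20% | 1.990% | 2.74 | 1.69–3.80 |

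With receipt reversed (50% for Fluarix Tetra, 90% for others), the ratio is 3.475/5.455 = 0.64.

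**Against sampling error.** Take the expected 5,000 subjects with an assumed split of 4,000 Fluarix Tetra and 1,000 others. At 90% versus 50% receipt, the exact 95% intervals without cluster adjustment are 4.77–6.20% and 2.43–4.81%, almost separate. At 90% versus 20% they are 4.77–6.20% and 1.22–3.06%, fully separate.

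**After splitting by receipt.** In the second model the received stratum has rate m + (1 − m) × q × a = 0.01 + 0.99 × 0.05 = 5.95% in both groups. The not-received stratum has m = 1% in both. The ratio is 1.00 in each stratum, whatever the receipt.

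**The case against.** Pooling is the declared secondary endpoint. Both documents define it as card-derived plus medically attended events, and subjects without a card are kept so that routine data can cover them. That stands. The point concerns reading the result by brand.

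Several safeguards deserve credit:

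- The primary brand rates are restricted to card recipients.
- SAP 7.3.1 would expose an imbalance in receipt.
- SAP 7.3.6.2 gives card-reported rates among returners.
- SAP 7.3.7 gives EHR-based rates by vaccine group in about 170 network practices. Card distribution is described only for the 10 enrolled practices, so this is largely a card-free view.
- The Protocol synopsis says that weekly outputs will list consultation-reported and card-reported events.

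None of these splits the pooled rates of the 10 practices by card receipt. The separate table-shell document is not available, so the final layout cannot be checked.

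A reader might infer that the bias definitely runs against Fluarix Tetra. The documents do not support that. They give no receipt or outside brand mix by group, and the bias reverses if receipt is lower for Fluarix Tetra. SAP 3.5 also has a separate unknown-brand group. Outside vaccinations with no recorded brand would go there, which weakens the Fluarix Tetra versus non-GSK contrast. Some outside vaccinees may hold a card, since the card asks where vaccination took place.

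All analyses are descriptive and no test or decision rule rests on the secondary rate. That limits the consequence without removing it.

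**Conclusion.** The concern holds as a limit on interpretation. The pooled secondary rates and the interim weekly rates can differ by brand with no true difference in reactogenicity whenever card receipt differs by vaccine group, and the plan neither separates the two kinds of ascertainment nor warns of this.

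The size is illustrative. Ratios of 1.23 and 1.74 follow from assumed event rates and receipt. The second model takes only the 50% return from the documents. An excess for Fluarix Tetra is the most plausible direction, inferred from practice selection alone.

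It would also go too far to infer that the primary brand rates carry this bias, since their denominator is card recipients only. The change is a worthwhile and inexpensive improvement. It does not repair a failed primary analysis.

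**What to change.** 1. In SAP 7.3.3, for the Weeks 35-48 cumulative rates of any AEI and each AEI category, add rows by card receipt (received / not received) within each vaccine group, beside the pooled rate.
2. In the weekly reports (SAP 9.1.1), add the same split for the any-AEI rate only.
3. State that pooled brand rates are not to be compared where SAP 7.3.1 shows receipt differing by vaccine group. Brand statements then rest on the receipt-specific rates, which remain unadjusted for age, risk status and practice.

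**Cost.** Receipt is already needed for the primary denominator, so no new data are required. Any AEI plus nine categories, four vaccine groups and two strata make 10 × 4 × 2 = 80 further rates in the final report, plus a few per weekly report. Splitting every AEI by week, age and risk status is not needed. The no-card stratum may be sparse, with wide intervals, and the card-received rows will largely follow the primary analysis, adding only medically attended events.
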